9.2.2. Missing and Partial AE Dates

Due diligence will be done to obtain accurate AE information. If all planned methods to obtain accurate AE information have failed, missing and partial AE onset and end dates will be imputed. Imputed dates will be flagged in the individual supportive subject listings. Unless otherwise specified, the following conventions will be used:

Missing and Partial AE onset dates

- If onset date is completely missing, then onset date is set to date of first dose
- If onset year is present and
 - month and day are missing:
 - If onset year = year of first dose, then set onset date to date of first dose

- If onset year < year of first dose, then set onset month and day to December 31st.
- If onset year > year of first dose, then set onset month and day to January 1st
- month is missing:
 - If onset year = year of first dose, then set onset date to date of first dose
 - If onset year < year of first dose, then set onset month to December
 - If onset year > year of first dose, then set onset month to January
- If onset month and year are present and day is missing:
 - If onset year = year of first dose and
 - onset month = month of first dose then set onset date to date of first dose
 - onset month < month of first dose then set onset date to last day of month
 - onset month > month of first dose then set onset date to 1st day of month
 - If onset year < year of first dose then set onset date to last day of month
 - If onset year > year of first dose then set onset date to 1st day of month
- For all other cases, set onset date to date of first dose

Missing and Partial AE end dates

- If end date is completely missing, end date is not imputed and the AE is flagged as “ongoing”
- If year is present and
 - month and day are missing:
 - If year = year of last dose, then set end date to the date of last dose
 - If year < year of last dose, then set end month and day to December 31st
 - If year > year of last dose, then set end month and day to January 1st
 - month is missing:
 - If year = year of last dose, then set end date to date of last dose
 - If year < year of last dose, then set end month to December
 - If year > year of last dose, then set end month to January
- If month and year are present and day is missing:
 - If year = year of last dose and
 - month = month of last dose then set day to day of last dose
 - month < month of last dose then set day to last day of month

- month > month of last dose then set day to 1st day of month
- If year < year of last dose, then set end date to last day of the month
- If year > year of last dose, then set end date to 1st day of month
- For all other cases, set end date to date of last dose

9.2.3. Summaries of Adverse Incidence Rates for Serious Adverse Events (SAE), adverse events leading to discontinuation, and treatment-related emergent adverse events

The number and percentage of TEAEs, SAEs, AEs leading to discontinuation, treatment-related emergent AEs and treatment-related emergent SAEs will be summarized by SOC, PT, and treatment group. The percentages will be calculated as the number of subjects with AEs divided by the number of subjects in each treatment in the safety analysis set. Tables of the number and percentage of subjects and the number of AEs by intensity and by relationship to study medication will also be presented.

Any withdrawals will be listed and summarized by reason for withdrawal, treatment and by any other relevant categorical information.

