9.2. Adverse Event Preferred Term and Body/Organ System Summary Tables

9.2.1. Summaries of Adverse Event Incidence Rates for All Subjects

Adverse events will be coded using Medical Dictionary for Regulatory Activities (MedDRA) version 21.0.

All AEs will be displayed in listings.

Any AE that occurs during the placebo run-in period will be summarized separately from the AEs occurring during the randomized treatment period. Any AE that occurs pre-run-in (between the subjects signing informed consent and administration of the first dose of the run-in study medication) will be listed. Adverse events occurring after the first dose of the randomized study medication will be defined as treatment-emergent adverse events (TEAEs).

A comparison of the incidence rate of AEs between study treatment groups will be presented overall, occurring in greater or equal to 1%, 2%, 3%, as well as AEs occurring in the study treatment arm in higher frequency than in placebo arm. Incidence rate is determined by the number of subjects with AEs divided by the total duration (day) of treatment across all subjects in given treatment group, multiplied by 100.

Summaries of the number of subjects with TEAEs and the number of TEAEs experienced will be presented by treatment. The number of subjects and the number of TEAEs will be presented using frequency counts and percentages, overall and by system organ class (SOC) and preferred term (PT). The percentages will be calculated as the number of subjects with TEAEs divided by the number of subjects in each treatment in the safety analysis set. Tables of the number and percentage of subjects and the number of TEAEs by intensity and by relationship to study medication will also be presented. If severity of an event is missing, then set AE severity as "Severe". If relationship to study treatment is missing, then set relationship as "Related". Similar tables will be created for treatment related emergent AEs (TREAEs). Events will be assigned to the study treatment administered prior to the start of the TEAE. Events that occurred during discharge and final follow-up will be assigned to the study treatment administered prior to the start of the event.

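### SAP 9.2.2 imputes AE onset and end dates without checking one against the other, so an event recorded as over before randomized dosing can be dated to Day 1

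*SAP*

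**What the plan says.** SAP 9.2.2 applies after attempts to obtain the real date have failed. For onset it sends several situations to the same date:

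- nothing known: "If onset date is completely missing, then onset date is set to date of first dose";
- month missing, or month and day both missing: "If onset year = year of first dose, then set onset date to date of first dose";
- day missing, same month and year as dosing: "onset month = month of first dose then set onset date to date of first dose";
- anything not covered: "For all other cases, set onset date to date of first dose".

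An onset month before the dosing month is handled differently: "onset month < month of first dose then set onset date to last day of month". End dates have their own list, keyed to the last dose, for example "month = month of last dose then set day to day of last dose". Neither list refers to the other. Imputed dates are flagged in the subject listings.

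SAP 9.2.1 says: "Any AE that occurs during the placebo run-in period will be summarized separately from the AEs occurring during the randomized treatment period". It defines a treatment-emergent AE (TEAE) as one occurring after the first dose of randomized medication. Protocol 13.8.3 likewise treats events between consent and the first randomized dose as pre-treatment. The shell for Listing 16.2.7.1 computes duration as stop date minus start date plus one.

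**The concern.** Defaulting an unknown onset to the first dose is a sensible conservative rule when the event might have begun on treatment. It is wrong when the record already shows that the event was over before treatment began. By the plan's own definitions that event belongs in the run-in or pre-run-in display, yet the rule dates it to Day 1.

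The consequences are extra TEAEs, a depleted run-in summary, and listings in which an event ends before it starts. Small counts can be visible because SAP 9.2.1 tabulates TEAEs at 1%, 2% and 3% cut-offs. With 225 subjects per arm, 2 subjects are 2/225 = 0.9% and 3 are 3/225 = 1.3%, so one reassigned event can bring a preferred term into the 1% table. A causality mark can travel with the event, since Protocol 11.3 forces a negative answer only before any study or run-in medication has been taken.

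**Working it through.** The plan gives no figure to reproduce here. The check applies the 9.2.2 rules literally.

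**1. Onset example (dates assumed).** First randomized dose 20 Sep 2018; AE end recorded as 14 Sep 2018.

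| Onset as recorded | Imputed onset | Duration (stop − start + 1) |
|---|---|---|
| Sep 2018, day missing | 20 Sep | 14 − 20 + 1 = −5 |
| completely missing | 20 Sep | −5 |
| 2018, month and day missing | 20 Sep | −5 |
| 2018, month missing | 20 Sep | −5 |

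An event that ended on 19 Sep, the day before dosing, gets 19 − 20 + 1 = 0.

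**2. Earlier-month branch.** First dose 5 Sep, onset August with day missing: the onset becomes 31 Aug, so the event is correctly not treatment-emergent. If it ended on 29 Aug, the onset still follows the end: 29 − 31 + 1 = −1.

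**3. End-date example.** The last dose is the evening before Visit 4 (Protocol 9.5). With first dose 20 Sep, Day 14 is 3 Oct and Visit 4 on Day 15 is 4 Oct. An AE starting on 4 Oct, with its end recorded as October and the day missing, is given 3 Oct. Duration is 3 − 4 + 1 = 0.

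**4. How often the same-month branch applies.** Inputs: run-in length L of 7 to 10 days (Protocol 6.1); Day 1 assumed uniform over a 365-day year. An AE starting s days before Day 1 and ending before Day 1 has s possible end days, so there are L(L+1)/2 start–end pairs: 28 for L = 7 and 55 for L = 10. If Day 1 is day d of its month, the pairs moved to Day 1 number k(k+1)/2, where k = min(d − 1, L).

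- L = 7: the first seven days of a month contribute 0+1+3+6+10+15+21 = 56; each later day contributes 28. Over the year: (12 × 56 + 281 × 28)/(365 × 28) = 8,540/10,220 = 84%.
- L = 10: the first ten days contribute 0+1+3+6+10+15+21+28+36+45 = 165; each later day contributes 55. Over the year: (12 × 165 + 245 × 55)/(365 × 55) = 15,455/20,075 = 77%.

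Counting the earlier-month branch as well, enumeration of the same pairs puts the imputed onset after the recorded end in 90% (L = 7) and 87% (L = 10).

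**5. The other reading of *first dose*.** If it meant the first run-in dose, say 10 Sep in example 1, the imputed onset would be 10 Sep. That is before the 14 Sep end and not treatment-emergent.

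**The case against.** The best defence is that this is a last-resort rule. Sites ask about AEs at every visit (Protocol 11.4.1), visits are about a week apart, and imputation starts only after due diligence fails. Imputed dates are flagged. Leaning towards treatment-emergent also matches SAP 9.2.1, which sets missing severity to severe and missing relationship to related. All of this limits the number of affected events. It does not change how they are classified in the tables, because the flag appears only in listings, and it does not justify overriding a known end date.

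Second, SAP 9.2.2 does not say which first dose it means, although 9.2.1 names both a run-in and a randomized one. The TEAE definition also says after the first dose, while the imputed value is a date without a time. Both points stand. The TEAE consequence is therefore conditional on the randomized-dose reading and on counting a Day 1 onset as treatment-emergent, which is usual practice but not stated.

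Third, the end-date fault is remote. No follow-up visit is planned, and a completely missing end date is left as ongoing. It needs a late onset and a partial end date together.

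A reader might go further and infer that the run-in nearly always shares Day 1's month. In a 30-day month the whole run-in does so only when Day 1 is the 8th or later (23/30 = 77%) for 7 days, or the 11th or later (20/30 = 67%) for 10 days. A reader might also infer that the rule biases the safety comparison. Run-in events precede randomization, so on average they add equally to both arms: the expected difference is unchanged and only a ratio moves slightly towards 1. The protocol's safety analyses are descriptive.

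**Conclusion.** The defect holds on a literal reading: 9.2.2 lets an imputed onset fall after a recorded end, and an imputed end fall before an onset. With *first dose* read as the first randomized dose, events known to have ended beforehand are dated to Day 1 and would ordinarily enter the TEAE tables, contrary to 9.2.1.

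The 77–84% is a share of AEs that start and end within the run-in and lack an onset day, assuming Day 1 is uniform over the calendar and all start–end pairs are equally likely. It is not an expected count; the documents give no rate of missing AE dates. This is a minor correction to safety reporting, with no bearing on the efficacy analysis.

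**What to change.** Keep every existing branch of SAP 9.2.2 and add three statements:

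1. If the recorded end date, or the latest possible date when the end is partial, is earlier than the imputed onset, set the onset to that end date. If that date is before the first randomized dose, class the AE as run-in or pre-run-in as appropriate.
2. An imputed end date may not be earlier than the onset date; use the later of the two.
3. Replace *first dose* with *first randomized dose* throughout.

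In the first example the onset becomes 14 Sep, the duration 1 day, and the event falls in the run-in summary. The additions should not become a blanket default to the first randomized dose, since that would move a day-missing August onset forward to a September Day 1 and create a false TEAE. The check should rest on the end date, because the AE listing shell has no reporting-visit field. The cost is two or three sentences and minor programming.

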9.3. Total Duration of Therapy, treatment Compliance and diary compliance

The number of subjects exposed to each study treatment will be summarized.

The number of days on treatment and the number of days on study (including run-in period and treatment periods) will be summarized by study treatment.

Treatment compliance will be calculated (the total number of doses actually taken / total number of doses expected*100). For subjects who have completed the study:

			Compliance Criteria	
Study Period	Duration	Scheduled Doses	Not more than 125% (doses)	Not less than 75% (doses)
Randomized Treatment	14 Days	28	35	21

For subjects who are early terminated, treatment compliance will be determined from their duration on treatment, up to the time they are considered completed or early terminated. If a patient is on randomized treatment for more than 14 days, use 14 as denominator to determine treatment compliance. Subjects taking fewer than 75% or more than 125% of the required doses will be considered non-compliant with dosing.

In addition, treatment compliance will be classified into four categories (<75%, >=75% - <=100%, >100% - <=125%, >125%). Treatment compliance will be summarized by category and study treatment.

Diary compliance (number of diary entry missed by visit) will only be presented in the listing.

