AM = morning; AR = allergic rhinitis; DV = discontinuation visit; eCRF = electronic Case Report Form; ENT = Ear, Nose and Throat; FV = final visit; HIPAA = Health Insurance Portability and Accountability Act; NS = nasal spray; PM = evening; PRQLQ = Pediatric Rhinoconjunctivitis Quality of Life Questionnaire; RV = randomization visit; RAST = radioallergosorbent test; SV = screening visit; TV = treatment visit.

- ^a The following visit windows are permitted: ±2 days for the TV (Visit 3) and +2 days for the FV.
- ^b Focused nasal exams will be performed to assess signs of AR as well as known complications of intranasal corticosteroid or antihistamine use (ie, bleeding, perforation and ulceration). Throat examination will be conducted to evaluate the evidence of throat irritation and candidiasis. If clinically significant (as judged by the Investigator) nasal ulceration, nasal mucosal erosion, and nasal septal perforation are observed at any visit, the subject should be referred to a qualified ENT specialist or other medically qualified specialist (qualified to evaluate and record these conditions, as judged by the Investigator) for further evaluation. A record from the specialists for such subjects should be maintained including the photographic evidence (imaging of nasal mucosa) of the assessment to allow pre- and post-treatment comparisons for AEs (See details in Section 11.1.7). The Sponsor (or designee) will collect the de-identified information as part of the study data collection. Eligibility of the subject for participation/continued participation in the study will be at the Investigator's discretion based on whether or not the protocol-defined selection criteria are met. These subjects may need to be rescreened due to delay in scheduling an ENT visit to obtain the necessary evaluation, as applicable, upon consultation with the Sponsor's study team and approval.
- ^c Documentation of a positive result within 12 months before SV is acceptable to meet the eligibility criteria. Intradermal and/or RAST will not be accepted.

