- ^d Subjects will assess their symptoms (with the help of parents/guardians/caregivers, if needed) at specified clinic visit, as directed by the site personnel. Subject will also assess their symptoms (with the help of parents/guardians/caregivers, if needed) at home every morning and evening prior to self-administering the study medication (with the help of parents/guardians/caregivers, if needed). Study medication during the placebo run-in and treatment periods should be taken immediately following the completion of the AM or PM diary assessment (with assistance from parents/guardians/caregivers, as needed) except on the morning of the RV and TV where the study medication should be administered at the study site under the supervision of site personnel.
- ^e All subjects must be told to refrain from taking their study medication on the mornings of the RV (Visit 2) and TV (Visit 3). They will administer the study medication at the clinic under the supervision of the study personnel. At TV (Visit 3), the subject is required to bring back their study drug assigned at Visit 2 and use the same bottle for administering the study drug under the supervision of study personnel. If the subject did take study drug on the morning of the TV (Visit 3) at home, then the date/time of the dose must be recorded but a second dose should not be administered at the clinic. The last dose of the study medication should be the PM dose on the day before the FV/DV (Visit 4). Subjects should be reminded not to take study drug on the morning of the FV/DV (Visit 4). If the subject did take study drug on the morning of the FV/DV (Visit 4), then the date/time of the dose must be recorded in the eCRF.

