9.4. Study Drug Preparation

9.5. Administration

Each study medication bottle will contain [REDACTED] metered sprays. The study medication will be dispensed to the subjects (parents/caregivers/legal guardians, as applicable) at the study site after adequate training using a placebo NS bottle.

The subjects (with the assistance from parents/caregivers/legal guardians, as needed) will be asked to take their daily double-blind, study medication for a period of 14 days (2 weeks) following a 7 to 10 day, single-blind, placebo run-in period. The first dose (AM dose on Day 1) will be administered in the clinic at the Randomization Visit (Visit 2). The AM dose of the day of the Treatment Visit (Visit 3) will also be administered at the clinic. All other doses will be self-administered at home (with assistance from parents/guardians/caregivers, as needed). The last scheduled dose will be the PM dose on the day before the Final Visit/Discontinuation Visit (Visit 4). Study drug should not be taken (either at home or at the clinic) on the morning of the Final Visit/Discontinuation Visit (Visit 4).

Subjects will self-administer the study medication during specified study visits under the supervision of the study personnel (with assistance from parents/guardians/caregivers, as needed). Additionally, subjects will self-administer the study medication at home BID per the subject instructions provided during the single blind placebo run-in period and the treatment period (with assistance from parents/guardians/caregivers, as needed). Subjects (parents/legal guardians/caregivers, as needed) will be adequately trained in the proper use of the study medication NS bottle at the specified visits as well as reviewing the subject study medication instructions.

Detailed instructions for the proper use of the treatment NS bottles are provided in Appendix I.

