6.7.4. Visit Windows

Subject participation may be 22 days up to 27 days with 7 to 10 days of a screening/run-in period and a 14-day treatment period, with allowable window periods for the study visits. The following visit windows are permitted: ± 2 days for the Treatment Visit (Visit 3) and ± 2 days for the Final Visit/Discontinuation Visit (Visit 4). However, only data up to Day 15 AM is to be included in the efficacy analysis of subject-reported nasal and non-nasal symptoms.

Table 2: Visit Windows (Days)

Visit	Relative Target Day	Visit Window
Visit 1 (Screening)	-7	-10 – -7
Visit 2 (Randomization)	1	1
Visit 3 (Treatment)	8	6 – 10
Visit 4 (Final/Discontinuation)	15	15 – 17

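### SAP 9.3 caps the compliance denominator at 14 days but not the doses counted, so compliance is overstated if dosing runs on to a Day 16 or 17 final visit

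*SAP*

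**What the plan says.** SAP 9.3 defines treatment compliance as "the total number of doses actually taken / total number of doses expected*100". For completers it tabulates 14 days, 28 scheduled doses, an upper limit of 35 doses and a lower limit of 21. For early terminations the expected number follows time on treatment. For longer treatment the rule is: "If a patient is on randomized treatment for more than 14 days, use 14 as denominator to determine treatment compliance". It then states: "Subjects taking fewer than 75% or more than 125% of the required doses will be considered non-compliant with dosing". SAP 6.5.3 lists compliance outside 75% to 125% among the deviations that may exclude a child from the PPS. SAP Table 14.3.2.5.1 reports four compliance categories, one of them above 100% and up to 125%.

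The protocol describes the end of dosing in two ways. Section 9.5 asks children to take "study medication for a period of 14 days (2 weeks"), but the same section says "The last scheduled dose will be the PM dose on the day before the Final Visit/Discontinuation Visit (Visit 4"). Footnote e of the Schedule of Assessments repeats the second rule: "The last dose of the study medication should be the PM dose on the day before the FV/DV (Visit 4"). Footnote a allows plus or minus "2 days for the TV (Visit 3) and +2 days for the FV", and Table 2 of the SAP accordingly puts Visit 4 on Day 15 to 17.

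**The concern.** The SAP foresees treatment beyond 14 days and fixes the denominator for it, but leaves the numerator as all doses actually taken. A child who follows the last-dose rule to a late Visit 4 is therefore scored on up to 16 days of doses against a 14-day requirement.

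Two things are at stake. First, the category above 100% would mix fully adherent children who had a late visit with children who took extra doses, so it would no longer identify over-use. Second, some children below 75% of what they were scheduled to take would meet the 75% limit and so would not be flagged for PPS exclusion on that criterion.

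No other section supplies the missing limit. The cut-off in SAP 6.7.4 concerns symptom scores: "only data up to Day 15 AM is to be included in the efficacy analysis of subject-reported nasal and non-nasal symptoms". It does not mention doses.

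**Working it through.** **Inputs.** Two doses a day, the first on the morning of Day 1 (Protocol 9.5). Last dose on the evening before Visit 4 (Protocol 9.5 and footnote e). Visit 4 on Day 15 to 17 (footnote a; SAP Table 2). Denominator of 14 days, with limits of 75% and 125% (SAP 9.3).

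**The plan's own figures.** 14 × 2 = 28 doses; 28 × 1.25 = 35; 28 × 0.75 = 21. All three match the SAP 9.3 table. The capping sentence says 14, not 28. I read it as 14 days, hence 28 doses, because dividing a dose count by 14 would score normal use at about 200%.

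**Doses scheduled under the last-dose rule.** 2 × (Visit 4 day − 1).

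**Score under the literal rule.** All randomized doses taken / 28 × 100.

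| Visit 4 | Doses scheduled | Score at full adherence | Counts that meet the 75% limit but are below 75% of the schedule |
|---|---|---|---|
| Day 15 | 28 | 28/28 = 100.0% | none |
| Day 16 | 30 | 30/28 = 107.1% | 21 (21/30 = 70.0%, scored 75.0%); 22 (22/30 = 73.3%, scored 78.6%) |
| Day 17 | 32 | 32/28 = 114.3% | 21 (21/32 = 65.6%, scored 75.0%); 22 (22/32 = 68.8%, scored 78.6%); 23 (23/32 = 71.9%, scored 82.1%) |

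**Upper limit.** The largest scheduled count, 32, is below 35, so a fully adherent child is never classed above 125%. Only a child who takes extra doses can cross that line. For example, 36 doses against 32 scheduled is 112.5% of schedule but scores 36/28 = 128.6%.

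**Against the 14-day course alone.** A child with a Day 17 visit who took 17 of the first 28 doses (60.7%) and all 4 later ones has 21 doses and scores 21/28 = 75.0%. That child is below 75% of the 14-day course and, at 21/32 = 65.6%, below 75% of the whole schedule.

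**The case against.** The strongest reply is that this is a chosen convention. The SAP sets the requirement at 28 doses, foresees longer treatment, and declines to use 30 or 32 as the denominator; on those terms, 21 doses is 75% of the required course. The 125% limit is also wide enough that no fully adherent child is lost. The second part stands. The first would stand only if the doses counted also came from the 14-day course, and the SAP does not say so: in the last example above, later doses make up for a shortfall within the course.

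A second reply is that treatment is described as 14 days throughout, and the shell of Listing 16.2.6.1, which carries dosing times, ends at Day 14. If dosing stops on the evening of Day 14, 28 is right and nothing is wrong. That is correct, and the finding is conditional on it. But the last-dose rule and the SAP's own sentence on treatment beyond 14 days both allow for longer dosing.

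A reader might also infer that compliance can be understated, because Listing 16.2.5.2 shows only missed doses and a programmer could subtract them from 28. The documents do not support this. The stated numerator is doses actually taken, no subtraction formula appears anywhere, and a listing shell shows what is printed, not how a variable is derived.

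**Conclusion.** The point holds, and it is minor. Read as written, SAP 9.3 overstates compliance for any child who keeps dosing to a Day 16 or 17 final visit. A fully adherent child is reported at 107.1% or 114.3%, and 21 to 22 of 30 or 21 to 23 of 32 doses meet the 75% limit. This assumes two doses a day, dosing up to the evening before Visit 4, and a numerator that includes every randomized dose.

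The reach is limited. It affects one descriptive table and, because SAP 6.5.3 leaves major deviations to the blinded data review, possibly membership of the PPS. Fully adherent children stay in the PPS. Interpretation rests on the FAS, where compliance plays no part, so the documents give no support for inferring that the primary result is at risk. Nor can a misclassification rate be given: neither the number of late visits nor the expected adherence is stated.

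**What to change.** Amend SAP 9.3 so that numerator and denominator cover the same doses, for example: *Compliance = doses taken from Day 1 AM to Day 14 PM / 28 × 100; for subjects terminated earlier, the denominator is the doses scheduled up to termination.* This keeps the limits of 28, 35 and 21 and fits the Day 15 AM cut-off already used for the diary scores. State the data source for doses taken, such as the daily AM and PM dosing times behind Listing 16.2.6.1; Listing 16.2.5.1 counts bottles, which is not enough. Add a column to Listing 16.2.5.2 for doses taken after Day 14 PM, since it has none for doses taken.

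The cost is a sentence or two, one derivation and one listing column. The drawback is that later doses no longer count. A child with a Day 17 visit who took 20 of the first 28 doses and all 4 later ones has taken 24/32 = 75.0% of the schedule but would score 20/28 = 71.4%. Days on treatment in Table 14.3.2.5.1 does not count doses, so it cannot replace the new column.

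This is a counting rule only. The 14-day text and the last-dose rule in Protocol 9.5 and footnote e conflict when Visit 4 is late, and the sponsor must reconcile them separately.
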